Duration of administration	continuously during the study and for 90 days after the last dose of treatment. Subjects will be followed until all treatment related adverse events have recovered to baseline or are deemed irreversible by the investigator. Subjects who are removed from study for reasons other than progression of disease will be followed every 3 months with imaging to evaluate disease status and survival analysis while the study remains open. Continuous treatment, on 21 day cycles. Treatment will be continued until confirmed radiographic disease progression, intolerable side effects, or ongoing response at 2
Reference therapy	years of therapy. The reference therapy is salvage TKI therapy (sunitinib or regorafenib) in imatinib-refractory GIST patients, which has previously shown response rates of 7% and 5%, respectively.
Statistical Methodology	Definition of primary outcome/endpoint: The primary endpoint is the overall response rate as defined as the best response, confirmed at ≥4 weeks, within the first 24 weeks of the start of study therapy, using RECIST v1.1 criteria. Definition of secondary outcomes/endpoints: PFS is defined as time from registration to time of clinical or radiographic disease progression as defined by RECIST v1.1 criteria, or death. OS is defined as time from registration to time of death from any cause. Analytic plan for primary objective: We will estimate the response rate to combination therapy with epacadostat and pembrolizumab using the exact 95% confidence interval based on the binomial distribution. Analytic plan for secondary and exploratory objectives: • We will estimate the survival distribution for both PFS and OS endpoints using the Kaplan Meier method. The log rank test will be used to examine differences between survival curves. • For correlative studies we will apply either the Fisher's exact test or Wilcoxon rank sum test to examine the correlation between response status and markers for categorical and continuous variables, respectively.

Version Date: 11/09/2017

Sample size justification:

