3. BACKGROUND

3.1 Gastrointestinal Stromal Tumors (GIST)

Background on GIST:

Gastrointestinal stromal tumors (GIST) are the most common sarcomas of the digestive tract, with approximately 4,000 to 6,000 new cases diagnosed each year in the United States.¹ The majority of these tumors harbor activating KIT or PDGFR-alpha mutations, making them sensitive to targeted treatment with the tyrosine kinase inhibitor imatinib mesylate.² Imatinib has activity against KIT and PDGFR, and is considered first line therapy for non-operable and metastatic GIST. Treatment with imatinib in GIST leads to disease control in 70-85% of patients (overall response rate of 68.1%, and stable disease in 15.6%), with a median progression free survival (PFS) of 20-26 months.³⁻⁶ While targeted therapy with imatinib has significantly improved survival for patients with advanced GIST, about 14% of patients exhibit primary resistance to imatinib.⁴ In addition, the majority of patients will eventually acquire mutations in KIT or PDGFR leading to secondary resistance after an average of 2 years of initial imatinib therapy.⁷⁻⁹

Treatment for imatinib-refractory advanced GIST:

Effective treatment options for patients with imatinib-refractory GIST are limited. Sunitinib, an oral receptor tyrosine kinase inhibitor with activity against KIT, PDGFR, as well as VEGF receptors, FLT3, and RET, has been shown to improve progression free survival in patients with inoperable GIST who have failed imatinib therapy, and is now considered standard second-line treatment for advanced GIST. In a phase III randomized placebo-controlled study of sunitinib versus placebo in patients with imatinib-resistant advanced GIST, the sunitinib group had an overall median progression free survival of 27.3 weeks compared to 6.4 weeks in the placebo group. However, the overall response rate was only 7 percent in the sunitinib treated group, compared with 0 percent in the placebo group. Regorafenib, an oral multikinase inhibitor of KIT, PDGFR, VEGFR, RET, BRAF, and FGFR, has been studied as third line treatment in imatinib and sunitinib refractory patients, and has been shown to improve progression free survival from

0.9 months to 4.8 months (p < 0.0001), with an overall response rate of 4.5 percent. Given the overall low response rates to TKI therapy in the second-line setting and beyond, more effective therapies for imatinib-refractory GIST patients are needed.

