17. STATISTICAL CONSIDERATIONS

17.1. Study Endpoints and Analysis Plan

Definition of primary outcome/endpoint:

The primary endpoint is the overall response rate defined as the best response within the first 24 weeks of the start of study therapy using RECIST v. 1.1 that has been confirmed at a subsequent

time point (\geq 4 weeks).

Definition of secondary outcomes/endpoints:

PFS is defined as time from enrollment to time of clinical or radiographic disease progression as defined by RECIST v.1.1 criteria. OS is defined as time from enrollment to time of death from any cause.

Analytic plan for primary objective:

We will estimate the response rate to combination therapy with epacadostat and pembrolizumab using the exact 95% confidence interval based on the binomial distribution.

Analytic plan for secondary and exploratory objectives:

- We will estimate the survival distribution for both PFS and OS endpoints using the Kaplan Meier method. The log rank test will be used to examine differences between survival curves using prognostic markers such as KIT mutation status.
- For correlative studies we will apply either the Fisher's exact test or Wilcoxon rank sum test to examine the correlation between response status and markers for categorical and continuous variables, respectively. Because of the limited sample size, the biomarker data analysis is for exploratory research only.

Sample Size Justification

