The primary endpoint of this trial is the objective response rate defined as the best response within the first 24 weeks of the start of study therapy using RECIST v1.1 criteria, and that has been confirmed at a subsequent time point (≥4 weeks).. We will use a Simon mini-max two-stage design with a target objective response rate of 20%, compared to a historical response rate of 5% with salvage tyrosine kinase inhibitor monotherapy¹⁰, and the probabilities of type I and type II error set at 0.1 and 0.2 respectively. In the first stage, 12 patients will be accrued. If less than 1 patient achieves a response among the initial 12 patients, the study will be declared negative and terminated. If at least 1 patient achieves a response, an additional 9 patients will be accrued to the second stage for a total of 21 evaluable patients. If at least 3 total patients achieve a response, that treatment will be declared positive for attaining the primary endpoint. This study design yields at least 80% power to detect a 20% response rate (compared to the null hypothesis of 5%) at a significance level of 10%. There is a 54% chance of stopping at Stage 1 if the true confirmed response rate is at most 5% (null hypothesis). Accounting for 10% dropout, we will plan to enroll a total of 23 patients.

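### The log-rank comparisons of PFS and OS by marker need an exact reference distribution: with only 1 or 2 patients in a marker group, the chi-square p-value rejects too often

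*Combined protocol and SAP*

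**What the plan says.** Section 17.1, under the analytic plan for secondary and exploratory objectives, has two bullets. The first says "We will estimate the survival distribution for both PFS and OS endpoints using the Kaplan Meier method", and continues: "The log rank test will be used to examine differences between survival curves using prognostic markers such as KIT mutation status". In the synopsis (Statistical Methodology) the second sentence is only "The log rank test will be used to examine differences between survival curves". No significance level, sidedness, minimum group size, event count or small-sample version is given for this test. The second bullet plans Fisher's exact test or the Wilcoxon rank sum test for markers against response. It ends by describing the biomarker analysis as exploratory because the sample is small.

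On numbers, the plan says "In the first stage, 12 patients will be accrued" and "If less than 1 patient achieves a response among the initial 12 patients, the study will be declared negative and terminated". Otherwise "an additional 9 patients will be accrued to the second stage for a total of 21 evaluable patients", and "Accounting for 10% dropout, we will plan to enroll a total of 23 patients".

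On the marker, Section 3.1 says "The majority of these tumors harbor activating KIT or PDGFR-alpha mutations", without a percentage. Section 14.2.4 provides for KIT testing where the status is not already known.

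**The concern.** The log-rank statistic is referred to a chi-square distribution on the strength of a large-sample argument. That argument depends on the smaller group as well as on the total. With one or two patients in a group the null distribution is skewed and coarse, and an early event in that group gives a large statistic by chance.

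Elsewhere the plan uses small-sample methods: an exact binomial interval for the response rate and Fisher's test for categorical markers against response. The survival comparison, on the same patients and markers, is the exception. What is at stake is an apparent survival difference for a rare genotype that a reader takes at face value. Most false rejections go one way. In the simulation below with 2 of 23 patients and all events observed, 9.2 of the 10.4 percentage points came from the small group having more events than expected, so that it seemed to do worse.

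**Working it through.** **The plan's own figures.** The documents give no error rate for the log-rank test, so the design is the only figure to reproduce. Chance of stopping at stage 1 under the 5% null: 0.95^12 = 0.540, as stated. Type I error with at least 3 responses of 21: 0.3413 × 0.0712 (1 response in stage 1, at least 2 of the next 9) + 0.0988 × 0.3698 (2, then at least 1) + 0.0196 (3 or more in stage 1) = 0.080. The same sum at 20% gives power 0.803. The design is sound, and a final N of 12 is a realistic outcome.

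**Inputs.**
- N = 12, 21 or 23 (Section 17.1).
- Scans at weeks 6, 12, 18 and 24, then every 12 weeks (Section 5.1).
- Median PFS 16 to 27 weeks. Section 3.1 cites 27.3 weeks on sunitinib and 4.8 months on regorafenib (4.8 × 30.4 / 7 = 21 weeks); 16 weeks is an assumption.
- Median OS 80 weeks, an assumption close to the 19 months (about 82 weeks) that Section 3.1 cites for dasatinib.
- Censoring uniform between weeks 26 and 104, two-sided 5% level, and a smaller group of 1 to 5: all assumptions. If the minority KIT group made up 5 to 20% of patients, its expected size would be 0.6 to 2.4 of 12, or 1.2 to 4.6 of 23.

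**Statistic.** X² = (O − E)² / V, rejecting above 3.841. E sums d·Y1/Y over event times. V sums d·(Y − d)/(Y − 1)·(Y1/Y)·(1 − Y1/Y). Here d is the number of events, Y the number at risk and Y1 the number at risk in the small group.

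**One patient, by hand.** Take N = 12, all events observed and no ties.
- The single patient fails first: E = 1/12 = 0.0833, V = 0.0764, X² = 11.0.
- Second: E = 0.1742, V = 0.1590, X² = 4.29.
- Third: E = 0.2742, V = 0.2490, X² = 2.12.
- Last: E = 3.103, V = 1.538, X² = 2.88.

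Two of the 12 equally likely ranks reject, so the true size is 2/12 = 16.7%. The same calculation gives 3/21 = 14.3% and 3/23 = 13.0%.

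**Larger groups, by simulation under no effect** (30,000 to 60,000 trials per cell for most entries). Rejection rates in per cent, over N = 12, 21 and 23:

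| Small group | PFS on scan grid, median 16–27 weeks | OS, median 80 weeks | All events observed, no ties |
|---|---|---|---|
| 1 | about 8–11 (21-week median) | 13–16 | 13–17 |
| 2 | 8.0–8.7 | 7.1–8.0 | 9.0–10.4 |
| 3 | 6.6–7.4 | about 5–6 | 8.2–8.9 |
| 4 | about 6 | within 5–7 | 7.3–7.9 |

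The last column is the upper end. It has neither the ties that scheduled scans create nor any censoring.

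**What drives it.** At N = 21 to 23 with 2 patients in the group and a 21-week median, the rate is 9.9–10.1% with continuous event times and 8.3–8.7% on the scan grid. Ties lower the inflation; the small group causes it. With a median PFS of about 2 months, groups of 2 or 3 give 5.0–5.8%.

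**Permutation version.** Computing X² for every allocation of patients to groups kept the size at or below 5% throughout, and at about 2 to 5% with 2 patients in a group. With 1 of 12, the smallest possible p is 1/12 = 0.083.

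**The case against.** The strongest reply is that nothing depends on this p-value. The plan says only that differences will be examined. It sets no level and no decision rule for the test, and comparing survival by KIT status is not a listed objective. That stands. A reader might infer that significance will be claimed too often on the main secondary endpoints, but the documents do not support this: the secondary objectives concern PFS and OS in the whole cohort.

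Second, a reader might infer that the KIT split must be very uneven. Section 3.1 speaks of a majority with KIT or PDGFR-alpha mutations taken together and gives no share for KIT alone. Section 17.1 does not define the grouping, and a split by mutation type could be fairly even. The one marker prevalence given is PD-L1 at 29% (Section 3.4), or 6.1 of 21 and 6.7 of 23 patients. At a group size of 7 the rate is 5.5–6.6%. This also stands, so the point is conditional on a small group.

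Third, the result depends on the PFS assumed. Section 3.1 also cites a 2-month median in third-line disease, and Section 6.1 allows up to four prior therapies. At that median the inflation for PFS nearly disappears. Tied scan times are not a reason for concern either, since they work the other way.

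Fourth, the exploratory caveat refers to the biomarker analysis in general and can be read to cover KIT. That is a fair reading, but the sentence closes the response bullet, and a label does not correct a p-value. Finally, log-rank test is ordinary protocol wording and does not exclude an exact version. True, but it does not require one, and the chi-square version is the usual default.

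**Conclusion.** The point holds as an inexpensive improvement. If a marker group has 2 patients, the chi-square log-rank test at an assumed two-sided 5% level typically rejects about 7 to 9% of the time when there is no effect. With 1 patient it can reach about 16% for OS. With 3 patients, and with 4 or more, it is about 5 to 7%, which hardly matters. These sizes rest on the assumed level, split, medians and censoring. The documents support the medians only in part and give no split. It would go too far to conclude that marker comparisons in this trial are generally unreliable because of the test, or that any efficacy conclusion is at risk: the response-rate decision and the whole-cohort Kaplan-Meier estimates are unaffected.

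**What to change.** In Section 17.1 and in the synopsis, specify that marker comparisons of PFS and OS use a permutation (exact) log-rank test, with the p-value taken over all allocations of patients to the marker groups, or a large random sample of them. Add that when a group has a single patient the curves are shown without a p-value. Place the exploratory statement so that it clearly covers this bullet as well as the response bullet.

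The cost is a few lines of text and code, with no new data. The exact test is slightly conservative with 2 patients in a group (true size about 2 to 5%). It also assumes that censoring does not differ between marker groups, which is reasonable with one treatment arm and one follow-up schedule.

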17.2. Stratification Factors

Not Applicable.

Version Date: 11/09/2017

17.3. Reporting and Exclusions

All patients included in the study must be assessed for response to treatment, even if there are major protocol treatment deviations or if they are ineligible. Each patient will be assigned one of the following categories: 1) complete response, 2) partial response, 3) stable disease, 4) progressive disease, 5) early death from malignant disease, 6) early death from toxicity, 7) early death because of other cause, or 9) unknown (not assessable, insufficient data).

All of the patients who met the eligibility criteria (with the possible exception of those who received no study medication) will be included in the main analysis of the response rate. Patients in response categories 4-9 will be considered to have a treatment failure (disease progression). Thus, an incorrect treatment schedule or drug administration does not result in exclusion from the analysis of the response rate.

All conclusions should be based on all eligible patients. Sub-analyses may then be performed on the basis of a subset of patients, excluding those for whom major protocol deviations have been identified (e.g., early death due to other reasons, early discontinuation of treatment, major protocol violations, etc.). However, these sub-analyses may not serve as the basis for drawing conclusions concerning treatment efficacy, and the reasons for excluding patients from the analysis should be clearly reported. The 95% confidence intervals should also be provided.

18. PROTECTION OF HUMAN SUBJECTS

This study is to be conducted in accordance with applicable government regulations and Institutional research policies and procedures. An IND annual report will be submitted to the FDA in accordance with 21.CFR 312.33.

This protocol and any amendments will be submitted to a properly constituted Institutional Review Board (IRB), in agreement with local legal prescriptions, for formal approval of the study conduct. The decision of the IRB concerning the conduct of the study will be made in writing to the investigator and a copy of this decision will be obtained before commencement of this study.

All subjects for this study will be provided a consent form describing this study and providing sufficient information for subjects to make an informed decision about their participation in this study. This consent form will be submitted with the protocol for review and approval by the IRB for the study. The formal consent of a subject, using the IRB-approved consent form, must be obtained before that subject is submitted to any study procedure. This consent form must be signed by the subject or legally acceptable surrogate, as outlined in the IRB approved protocol, and the investigator-designated research professional obtaining the consent.

Version Date: 11/09/2017

19. STUDY FINANCES

19.1. Conflict of interest

Any investigator who has a conflict of interest with this study (patent ownership, royalties, or financial gain greater than the minimum allowable by their institution, etc.) must have the conflict reviewed by the Columbia University Conflict of Interest Committee with a Committee-sanctioned conflict management plan that has been reviewed and approved prior to participation in this study. All CUMC investigators will follow the University conflict of interest policy.

19.2. Subject Stipends or Payments

There are no subject stipends or payments.

20. PUBLICATION PLAN

Neither the complete nor any part of the results of the study carried out under this protocol, nor any of the information provided by the sponsor for the purposes of performing the study, will be published or passed on to any third party without the consent of the study sponsor. Any investigator involved with this study is obligated to provide the sponsor with complete test results and all data derived from the study.

21. GUIDELINES FOR AFFILIATE INSTITUTIONS IN MULTICENTER STUDIES

21.1. Multi-site Communication

The CPDM Office at CUMC provides administration, data management, and organizational support for the affiliate sites in the conduct of a multicenter clinical trial. The CPDM Office will coordinate regularly scheduled conference calls with affiliate sites.

The following issues will be discussed, as appropriate:

- Enrollment information
- Response assessments
- Adverse events (e.g., new adverse events and updates on unresolved adverse events and new safety information)
- Protocol violations
- Other issues affecting the conduct of the study

21.2. New Protocol Distribution, IRB Submission, Modifications, and Annual Renewals

- Protocol specific documents are distributed to affiliate sites once CUMC IRB approval has been obtained.
- The affiliate site must submit a draft of site specific revisions to protocol and/or consent form documents for review and approval by the sponsor-investigator prior to submission to the local IRB. Draft documents should be sent to the study specific email

Version Date: 11/09/2017

address. The site will be provided confirmation that they are approved to submit to their local IRB.

• Protocol amendments must be approved by the affiliate site's local IRB within 90 days of distribution to the site by the sponsor-investigator.

21.3. Regulatory Documents

Prior to Site Initiation:

Sponsor-Investigator will ensure that proper requests are made of sites and that the following documentation is collected, prior to the initiation of an affiliate site.

- CV of PI, Co-I's and other research staff listed on FDA 1572 (signed and dated copy within 2 years)
- Medical Licenses of PI and Co-I's (current copy)
- Human subjects training certificates for PI and Co-I's
- CLIA/Laboratory Certifications for Local Laboratories listed on FDA 1572
- Local Laboratory Director's CV and License
- Local Laboratory Reference Ranges
- IRB roster or statement of compliance
- FDA Form 1572, if applicable (wet ink originals required)
- Financial Disclosure forms for all members listed on FDA 1572 (wet ink originals required)

Ongoing Regulatory Documentation: Sponsor-Investigator will ensure that proper requests are made of sites and that the following documentation is collected throughout the course of the study.

- IRB approval letters for all protocol modifications and all renewals
- IRB-approved consent forms
- Current IRB roster, if statement of compliance is not provided as part of site initiation
- FDA Form 1572, if applicable as updates are required
- Updated investigator and site information where relevant (e.g., CV, medical licensure and Financial Disclosure for new sub-investigator, local laboratory information)

Regulatory documents may be sent to [contact] or to the following address:

Clinical Protocol & Data Management Office [name]

21.4. Site activation

Version Date: 11/09/2017

Columbia University will schedule a site initiation visit once IRB approval has been submitted from the affiliate site.

21.5. Central Registration Procedures- Affiliate Institution Research Participant Registration Process

All Affiliate Institutions **must** register subjects with the coordinating center (CUMC) **prior** to any administration of study drug/intervention/local institution registration. Please see instructions below:

- 1. Within 48 hours of obtaining consent (excluding holidays and weekends), the Affiliate Institution CRN and/or CRC is required to submit the following documents to the coordinating center's designee (CUMC Multicenter Core) via the study listserv [contact]. The coordinating center's designee will review the documents for accurateness, and subsequently submit the documents to the CPDM Central Registration Office via email at [contact] (or via fax at [contact]), with a request to register the patient "pending eligibility." The title of the email should read, "Pending Subject Registration Request (PHI)". The following documents should be submitted with the pending registration request, as applicable:
 - a. Redacted Completed/signed IRB approved/stamped Informed Consent Forms, including additional study ICFs (e.g., tissue, DNA, etc.), as applicable
 - b. Redacted Signed HIPAA (or institutional equivalent)
 - c. MCT CPDM Velos Note to File form
- 2. The Affiliate Institution's investigator/research nurse/data manager/coordinator must contact the coordinating center's designee (CUMC Multicenter Core) via telephone or email to communicate the following:
 - a. Notify of pending registration request
 - b. Confirm method of registration request submission (email or fax)
 - c. Communicate expected time-line of registration request submission (e.g., same day, next day, within the hour, etc.)
- 3. To complete registration, the Affiliate Institution's investigator/research nurse/data manager/coordinator should then submit the following documents to the CUMC study specific designee:
 - a. A signed Affiliate Site Eligibility Checklist (signed by the investigator)
 - b. Copies of redacted source documentation necessary for each item to be verified on the CUMC specific Eligibility Checklist, including but not limited to:
 - i. Copy of required laboratory test and procedure reports (e.g., hematology, serum chemistry, pregnancy test when applicable, MRI reports, CT/bone scans, etc.)
 - ii. Copy of pathology and surgical reports
 - iii. Copy of clinic note(s) capturing the consent process information, along with providing source documentation of any other items needed for screening/eligibility that are not captured in other source document forms.

Version Date: 11/09/2017

(e.g., positive investigator statements of unique eligibility items not captured via other direct source documentation, concomitant medication lists, etc.)

- iv. Protocol deviation/waiver approvals (if applicable)
- c. Please note: subject line of email or fax should include the following: "AAAR1581 Complete Subject Registration Request (PHI)".
- 4. Upon receipt of the above mentioned documents, the designated study specific Clinical Research Coordinator will review all documents and verify patient eligibility. If any questions arise during the review process, queries in the form of emails will be addressed to the applicable affiliate site study team personnel for clarification prior to enrollment. Upon verification, the CUMC Multicenter Core will then forward all documents to the CPDM Central Registration Office for central registration (as described above). The CPDM Central Registration Registrar will review all applicable documents and communicate to the CUMC study specific designee in order to clarify any items. The CUMC study specific designee will communicate with the applicable site study team personnel for additional clarifications necessary prior to enrollment.
- 5. Upon receipt of the subject registration notification email, the CUMC Multicenter Core will forward the notification email (which will include the study specific patient ID) to the affiliate site's Principal Investigator, Consenting Professional, and applicable research personnel. This notification should be filed in the patient research binder accordingly. Protocol therapy may not be initiated prior to receipt of this notification from the coordinating center.
- **6.** All screenfail/ineligible subjects, as well as subject's who withdraw consent prior to enrollment/initiation of protocol therapy must be submitted to the Central Registration Office in a manner analogous to the procedures noted above. Applicable source documentation will be required within the corresponding submissions.

21.6. Protocol Deviation/Subject Waiver request for Affiliate Sites:

The Affiliate site MUST submit a prospective deviation request to the CUMC lead PI for review and submission to the HICCC DSMC and CUMC IRB. Approvals must be obtained from all entities prior to implementation at the Affiliate site. If a prospective protocol deviation request is submitted for review (from an Affiliate site), the PI/site memo(s), HICCC DSMC approval(s) and correspondence and CUMC IRB approval letter(s)/equivalent should be forwarded to the Affiliate site for documentation. The Affiliate site is also required to obtain prospective local IRB approval as per institutional policies/procedures prior to implementing the proposed deviation and registering/enrolling the subject via CUMC Central Registration. All documents and determinations must be clearly documented in the study subject's medical record, research chart and regulatory binder, as described. Please note that the HICCC DSMC and PRMC do not approve eligibility deviations. If eligibility deviations are submitted, they will not be approved.

Version Date: 11/09/2017

